3.1.4 Cohort Review Committee

The CRC composition and duties are described in a separate Charter. A CRC meeting will be convened to review all safety data and decide whether DLTs were observed. Based on the CRC's adjudication of DLTs observed in a cohort, they will guide decisions on the dose level that the subsequent cohort will be administered.

A review of all relevant available data will occur between the Sponsor and participating institution(s) at least monthly for the duration of the study.

3.1.5 Definition of Dose-limiting Toxicities

Toxicity will be evaluated according to the National Cancer Institute (NCI) Common Terminology Criteria for AEs (CTCAE) v4.03 toxicity criteria. Dose-limiting toxicities are defined as those events that will require dose modification; therefore, DLT criteria should be referenced throughout the Phase 1 and 2 portions of the study. The DLT evaluation period will be Cycle 1 (Weeks 1 through 4).

For the purposes of dose level escalation and determination of the MTD(s), only DLTs (as defined below) that occur during the first cycle of treatment will be considered in decisions regarding dose level escalation; however, DLTs or other clinically significant toxicities that occur throughout the observation period will be considered when determining the RP2D(s) for use in this trial and in subsequent clinical trials.

During Cycle 1 of the dose escalation portion, if two of the three subjects in a cohort experience the same Grade 2, treatment-related AE, then subsequent increases in dose level will precede in increments less than 100%. If more than one cohort is treated at the same dose level and greater than 67% of subjects treated at that dose level experience the same Grade 2 treatment-related AE, dose level escalation will precede in increments less than 100%. In such a case, specific dose level increments will be decided by the CRC.

Protocol-defined hematologic DLTs include:

- CTCAE Grade 4 neutropenia \geq 7 days;
- CTCAE Grade 3 or 4 neutropenia with fever \geq 38.5°C;
- CTCAE Grade 3 thrombocytopenia with bleeding;
- CTCAE Grade 4 thrombocytopenia \geq 7 days.

Protocol-defined non-hematologic DLTs include:

- Grade \geq 3 vomiting or nausea \geq 14 days despite the use of optimal anti-emetic treatments;
- Grade \geq 3 diarrhea \geq 14 days despite the use of optimal anti-diarrheal treatments which should include infliximab as per institutional guidelines;
- Serum creatinine $>$ 3.0 x ULN;
- AST or ALT $>$ 5 x ULN; in subjects with liver metastasis who entered the study with Grade 2 elevation of AST or ALT, an AST or ALT increase \geq 50% relative to baseline and lasting \geq 1 week;
- Bilirubin \geq 3.0 x ULN;
- Bilirubin \geq 2.0 x ULN with ALT $>$ 3 x ULN in subjects without liver metastases;

Other non-hematologic toxicities of Grade \geq 3, except for the following:

- AEs related to underlying disease;
- CTCAE Grade 3 fatigue $<$ 14 days;
- Alopecia;
- Isolated, asymptomatic elevations in biochemistry laboratory values lasting \leq 14 days. This includes electrolyte abnormalities that respond to medical intervention.

Ipilimumab-related DLTs:

- Grade \geq 4 immune-mediated dermatitis (except skin reaction at site of injection);
- Grade \geq 3 immune-mediated endocrinopathy (with the exception of Grade 3 autoimmune thyroiditis that resolves to Grade 1 or baseline within 28 days of onset);
- Grade \geq 3 immune-mediated enterocolitis;

- Grade ≥ 3 immune-mediated hepatitis with the exception of Grade 3 immune-mediated hepatitis that resolves to Grade 1 or baseline within 28 days of onset;
- Grade ≥ 3 immune-mediated neuropathy, pancreatitis, meningitis, nephritis, and pneumonitis that are considered to be possibly, probably, or definitely related to study therapy as determined by the Investigator;
- Any persistent IMO-2125-related toxicity that leads to a delay of scheduled (per standard of care) ipilimumab > 14 days.

Pembrolizumab-related DLTs:

- Grade ≥ 3 pneumonitis or recurrent Grade 2 pneumonitis;
- Grade ≥ 3 nephritis;
- Grade ≥ 3 infusion-related reactions;
- Inability to reduce corticosteroid dose to 10 mg or less of prednisone or equivalent per day within 12 weeks;
- Any Grade ≥ 3 treatment-related AE that recurs.

If at any time during the study, a subject experiences a DLT as outlined above, the toxicity in question must be assessed for attribution based on the known toxicity profiles for ipilimumab, pembrolizumab, and IMO-2125. If assessment can be clearly attributed to one of the drugs in the combination, then dosing should be interrupted and the toxicity should be followed until resolution, stabilization, or return to baseline. Treatment with the other agent may continue during this time period. If attribution cannot be clearly ascribed to one agent versus the other, then both IMO-2125 and ipilimumab (or pembrolizumab) should be stopped and the toxicity should be followed until resolution, stabilization, or return to baseline. If treatment is to be resumed, then re-initiation criteria must be met. If the DLT was clearly related to IMO-2125 or if attribution cannot be clearly determined, then IMO-2125 must be administered at a lower dose level (a minimum reduction of at least 1 dose level). If the DLT recurs after a dose level reduction, then treatment should be discontinued.

Subjects who experience a non-laboratory, IMO-2125-related DLT must be evaluated weekly, at a minimum, until resolution to Grade ≤ 1 or baseline and then at least monthly until return to baseline or stabilization of the event, whichever comes first. For abnormal laboratory values that qualify as DLTs, subjects will be followed twice weekly until values return to Grade ≤ 1 or baseline, whichever comes first.

Criteria for re-initiation of study treatment following occurrence of a DLT are as follows:

ANC must be $\geq 1.5 \times 10^9/L$ (1500/ μ L);

Platelets must be $\geq 75 \times 10^9/L$ (75,000/ μ L);

All clinically significant non-hematologic toxicities for which a causal association to study treatment cannot be ruled out must be Grade ≤ 1 (except alopecia) or returned to baseline.

If the subject does not meet these criteria, dosing will be delayed and the subject should be re-evaluated within 48 to 72 hours. If the next cycle is delayed by more than 21 days for toxicity, the subject should be removed from study treatment. In these situations, if the subject is experiencing clinical benefit and has a favorable risk/benefit profile, study treatment with IMO-2125 may be continued if agreed upon by the Sponsor and the Investigator.

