3.1.3 Dose Escalation and Stopping Rules

Up to five dose levels for IMO-2125 are initially planned (**Table 2**).

Table 2: Treatment Doses to be investigated

Dose Level	IMO-2125	Ipilimumab	Pembrolizumab
-1	2 mg	3 mg/kg	200 mg
+1	4 mg	3 mg/kg	200 mg
+2	8 mg	3 mg/kg	200 mg
+3	16 mg	3 mg/kg	200 mg
+4	32 mg	3 mg/kg	200 mg

In Phase 1, the study will enroll subjects in planned cohorts of 3, beginning at Dose Level +1 for the ipilimumab treatment arm and beginning at Dose Level +2 for the pembrolizumab treatment arm once safety of the IMO-2125 + ipilimumab combination has been established for that level.

Additionally, if, due to observed toxicity, it proves difficult to provide IMO-2125 for 3 consecutive weeks in Cycle 1, the decision may be taken by the CRC to add cohorts where alternative schedules of IMO-2125 administration will be explored.

The MTD will be determined from the assessment of DLTs during the first treatment cycle of each cohort (Section 3.1.5). Using a prior beta(1,1) distribution of the DLT rate δ_i for each dose level i , the MTD is defined as the highest dose level for which the mean of the posterior distribution of toxicity is closest to 25% among all the evaluated doses i for which $\text{Pr}(\delta_i > 0.25 | \text{data}) < 0.80$.

The RP2D(s) will be selected from dose level(s) at or below the MTD. Additional dose levels may be studied if the MTD(s) have not been reached and pharmacodynamic activity is deemed to be inadequate. At the time of completion of the Phase 1 portion of the study an analysis of the data will be performed.

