3.1.3.1 Phase 2 Stopping Rules

Additional subjects will be enrolled at the RP2D level(s) established in the Phase 1 portion of the study for a total of approximately 90 to 100 subjects enrolled in the study. DLTs will be continuously monitored throughout the study. Assuming a prior beta (0.6, 1.4) distribution for the overall toxicity rate for a treatment, a Phase 2 arm will terminate if the $\text{Pr}(\delta_t > 0.25 | \text{data}) > 0.80$, where δ_t is the DLT rate attributable to the treatment. The decision rule for terminating due to toxicity is presented in **Table 3**. The method used to produce the decision rule and operating characteristics was designed by Thall (2006).

Table 3: Phase 2 Stopping Boundaries

If there are this many first-cycle DLTs or more	3	4	5	6	7	8	9	10
Stop if this many subjects (or fewer) have begun treatment	7	10	13	17	20	24	27	29

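### Bleeding makes thrombocytopenia a DLT only at Grade 3, so a short Grade 4 episode with low-grade bleeding on the Grade 4 days meets no listed criterion

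*SAP*

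**What the plan says.** SAP Section 3.1.5 gives two thrombocytopenia items among the hematologic DLTs: "CTCAE Grade 3 thrombocytopenia with bleeding", with no minimum duration, and "CTCAE Grade 4 thrombocytopenia" lasting at least 7 days. The corresponding neutropenia item is "CTCAE Grade 3 or 4 neutropenia with fever" of at least 38.5°C, which covers both grades.

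The same section limits what may count: "only DLTs (as defined below) that occur during the first cycle of treatment will be considered in decisions regarding dose level escalation". These counts are then used in two places:

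- **Section 3.1.3:** "the MTD is defined as the highest dose level for which the mean of the posterior distribution of toxicity is closest to 25" per cent, among doses with Pr(rate > 0.25) below 0.80 under a beta(1,1) prior.
- **Section 3.1.3.1, Table 3:** the row headed "If there are this many first-cycle DLTs or more" gives the Phase 2 toxicity boundaries, under a beta(0.6, 1.4) prior and a stopping limit of 0.80.

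Section 3.1.4 leaves adjudication to the committee: "A CRC meeting will be convened to review all safety data and decide whether DLTs were observed".

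**The concern.** Read literally, the list treats the worse platelet grade more leniently. Bleeding turns a Grade 3 count into a DLT immediately, while at Grade 4 bleeding plays no part and only duration matters. The SAP gives no reason for this. The neutropenia item shows that the authors name both grades when they mean both.

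An event that falls through would be left out of the Cycle 1 count used for escalation, the MTD and Table 3. In any cycle it would also fail to trigger the steps that Section 3.1.5 ties to a DLT: interruption, reduction of IMO-2125 by at least one dose level when the event is related or cannot be attributed, and the re-initiation criteria, which include a platelet threshold. The protocol may have other dosing rules that apply.

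**Working it through.** **Step 1. Does any listed item catch the event?** Take a first Grade 4 episode in Cycle 1, with bleeding only on the Grade 4 days.

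| Grade 4 duration | Bleeding grade | Grade 3 with bleeding | Grade 4, 7 days or more | Non-hematologic Grade 3 or higher |
|---|---|---|---|---|
| 3 or 6 days | 1 or 2 | no | no | no |
| 3 or 6 days | 3 | no | no | yes |
| 7 days | 1 or 2 | no | yes | no |
| 7 days | 3 | no | yes | yes |

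The arm-specific items in Section 3.1.5 add little. The ipilimumab item needs persistent IMO-2125-related toxicity that delays ipilimumab by more than 14 days. The pembrolizumab item needs a Grade 3 or higher treatment-related event that recurs, so a first episode does not qualify. The gap is the first row of the table.

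**Step 2. What can one uncounted event change?** With r DLTs in n subjects and prior beta(a, b), the posterior is beta(a + r, b + n − r) and its mean is (a + r)/(a + b + n).

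*MTD admissibility, beta(1,1), limit Pr(rate > 0.25) < 0.80:*

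- 2/3: beta(3,2), 0.949, inadmissible. Recorded as 1/3: beta(2,3), 0.738, admissible.
- 3/6 (6 subjects at a dose is assumed): beta(4,4), 0.929, inadmissible. Recorded as 2/6: beta(3,5), 0.756, admissible.

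*MTD choice:* the mean for 0/3 is 1/5 = 0.20, at distance 0.05 from 0.25. The mean for 1/3 is 2/5 = 0.40, at distance 0.15. Suppose the true counts are 0/3 at 16 mg and 1/3 at 32 mg, with no other dose closer to 25%. Both doses are admissible (0.316 and 0.738), and the MTD is 16 mg. If the single event is not counted, both means are 0.20, and choosing the highest of the tied doses gives 32 mg.

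*Phase 2, beta(0.6, 1.4):* the rule stops an arm when Pr(rate > 0.25) > 0.80. All eight Table 3 boundaries reproduce as stopping points.

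| DLTs / subjects at boundary | Pr(rate > 0.25) | With one DLT fewer |
|---|---|---|
| 3/7 | 0.820 | 0.560 |
| 4/10 | 0.829 | 0.617 |
| 5/13 | 0.839 | 0.661 |
| 6/17 | 0.811 | 0.643 |
| 7/20 | 0.826 | 0.678 |
| 8/24 | 0.807 | 0.664 |
| 9/27 | 0.822 | 0.694 |
| 10/29 | 0.863 | 0.756 |

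In every column, one DLT fewer moves the arm from stop to continue.

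These figures show what any single uncounted DLT does in this design. They say nothing about how often this particular event occurs.

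**The case against.** The strongest objection is that the SAP only restates a list it labels as defined by the protocol, and the protocol is not at hand. If the protocol has the same wording, the SAP copies it faithfully and the fault lies upstream. That stands, and it decides where the correction starts. It does not make the text sound.

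Second, the committee has room to count the event. The list is introduced as non-exhaustive, the CRC decides what is a DLT, and Section 3.1.5 opens by describing DLTs as events that require dose modification. Some of this stands, because a sensible committee might well count a bleeding Grade 4 event. But the opening sentence is circular, since dose modification in this SAP follows from meeting the listed items. The restriction to DLTs as defined in the list also pulls the other way. It is fair to say that this clause mainly separates first-cycle events from later ones.

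Third, platelets usually pass through Grade 3 while falling and recovering, so bleeding that extends into those days meets the Grade 3 item. That is right and narrows the gap. Scheduled Cycle 1 counts fall at Weeks 1, 2 and 3, with the next at Week 5 (Tables 4 and 5). Dating the bleeding against the platelet grade may therefore need unscheduled counts, and the classification could be uncertain.

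Fourth, no planned output depends on it. The DLT Evaluable Population serves only CRC meetings (Section 6), and Appendix E lists no DLT table. The event would still appear in the adverse event summaries and could be weighed in selecting the RP2D. All of this stands and limits the severity.

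**Conclusion.** The list is wrong as written, and the point is minor. Grade 4 thrombocytopenia of under 7 days, with Grade 1-2 bleeding only on the Grade 4 days, meets no listed DLT criterion, while the milder platelet grade with the same bleeding does.

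The reach is narrow: CRC escalation decisions, the MTD, Table 3 monitoring and the DLT-linked dosing steps. Efficacy analyses and planned tables are unaffected. Within that reach, one missed event can make an inadmissible dose admissible, raise the MTD by one level or keep a Phase 2 arm open, provided the count sits at a boundary.

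This rests on reading the list literally, on the CRC not counting the event by its own judgement, and on the assumption that the event is rare. Whether the SAP miscopied the protocol or shares its gap cannot be settled from the SAP alone.

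**What to change.** First check the protocol and the CRC charter. If they already name both grades, correct the SAP to match. If they share the gap, amend all three together. In Section 3.1.5, change the bleeding item to cover CTCAE Grade 3 or 4 thrombocytopenia with bleeding, and keep the separate Grade 4 item of at least 7 days.

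The cost is one bullet in the SAP, plus a wording change in the protocol and charter only if they have the same text. No assessment, table or listing is added. Section 3.1.1 shows that subjects had already been assigned under earlier protocol versions, so any Grade 4 platelet episodes already adjudicated should be looked at once against the corrected wording.

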3.1.6 Safety Assessment for Immunologically Related Toxicity

Based on an incidence of Grade 3 or greater immune-mediated AEs associated with use of ipilimumab or pembrolizumab of approximately 12% to 15%, the following safety precautions will be followed. Examples of relevant toxicities include the following: enterocolitis, hepatitis, dermatitis, neuropathy, endocrinopathy, nephritis, pneumonitis, pancreatitis, non-infectious myocarditis, uveitis, and iritis.

During dose level escalation, if any of the following is observed, the CRC will be convened to review all safety findings for all subjects treated in that cohort and all previous cohorts, including those events that occurred beyond Cycle 1, to guide next steps.

If more than one subject experiences a Grade ≥ 3 , immune-related adverse event (irAE) in a cohort of 3 subjects;

If more than two subjects experience a Grade ≥ 3 irAE in cohorts of 6 subjects.

During the Phase 2 portion of the trial, if the incidence of Grade ≥ 3 irAEs observed in Cycle 1 or in subsequent cycles of treatment exceeds 25%, the CRC will be convened to review all safety findings from all subjects treated in the study to guide next steps.

3.2 Duration of Study

3.2.1 Treatment Duration

The study treatment period is 29 weeks (as per Table 1) in the absence of intolerable toxicity or unequivocal disease progression. Continued treatment with pembrolizumab

following the completion of study treatment is at the discretion of the Investigator for subjects in the IMO-2125 + pembrolizumab treatment arm.

3.2.2 Study Duration and Study Completion

The study ends approximately 1 year after the last subject in Phase 2 has commenced study treatment. Subjects who complete or discontinue study treatment prior to progression will be followed for clinical and radiological evidence of progression and immunogenicity assessment at least every 3 months until documentation of RECIST v1.1 progressive disease (PD), start of a subsequent anti-cancer treatment regimen, withdrawal of consent, death, or Sponsor notification that follow-up is no longer required, whichever comes first. Best response to first subsequent therapy, AEs which are Grade ≥ 3 , and concomitant medications used to treat these AEs, will also be captured during the follow-up phase of the study (Table 4 and Table 5).

After documentation of PD or use of a subsequent anti-cancer treatment regimen, all subjects will be contacted by telephone every 3 months for a survival follow-up until the site is notified by the Sponsor that survival follow-up is no longer required. A subject has completed the study at the earliest of death or study end.

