Coagulation ¹⁰	X	X ₉			X	X	X			X		X		X	X
Chemistry profile	X	X ₉	X	X	X	X	X			X		X		X	X
Thyroid functions	X		X		X	X	X			X		X		X	X
CH50/C3/C4	X				X	X	X			X		X		X	X
Urinalysis	X					X				X					X
Vital signs ¹¹	X	X	X	X	X	X	X			X		X		X	X
ECG	X		X ₁₂				X ¹²								X
Directed physical ¹³	X	X			X	X	X			X		X		X	X
Pregnancy test	X														X
Tumor biopsies/biomarkers ¹⁴	X	X ₁₅	X			X		X				X			
Blood biomarkers		X ₁₆	X ₁₆			X ¹⁶									
Radiology	X					X ₁₇			X ₁₇				X ¹⁷		X ¹⁸
Response ¹⁹						X ₁₇			X ₁₇				X ¹⁷		X ¹⁸
PRO ²⁰		X				X			X				X		X ¹⁸
IMO-2125 dosing		X	X	X	X	X	X		X		X		X		
Ipilimumab dosing		X		X	X	X									
Pembrolizumab dosing			X		X	X	X		X	X	X	X	X	X ²¹	X ²¹
PK testing ²²		X	X	X	X	X	X		X ₂₃		X ₂₃		X ²³	X ²³	
Immunogenicity ²⁴		X			X		X		X		X		X	X	X ²⁵

Abbreviations: AE=adverse event; aPTT=activated partial thromboplastin time; C3=complement component 3; C4=complement component 4; CBC=complete blood count; CH50=total hemolytic complement activity 50; CR=complete response; CT=computed tomography; Demogr=Demographic; diff=differential; ECG=electrocardiogram; ECOG=Eastern Cooperative Oncology Group; EOT= End of Treatment; hx=history; INR=international normalized ratio; irRC=immune-related response criteria; med=medical; PK=pharmacokinetic; PR=partial response; PRO = patient reported outcomes; PT=prothrombin time

¹ Please note, the number of weeks per cycle varies. Cycle 1 is 4 weeks in length to account for an IMO-2125 priming dose. Cycles 2, 3, and 4 are 3 weeks in length, and Cycles 5, 6, and 7 are included as maintenance dosing and are 6 weeks in length.

² The Safety Follow-up Visit should be 21 days following the last dose of IMO-2125 (\pm 5 days).

³ Includes ongoing follow-up every 3 months until documented disease progression, next melanoma treatment, withdrawal of consent, death, or Sponsor notification that follow-up is no longer required.

⁴ All assessments and IMO-2125 dosing will occur within a \pm 2-day window. Ipilimumab and pembrolizumab will be dosed per their respective labels.

⁵ All Screening tests and assessments must be performed within 21 days of the start of Week 1 of Cycle 1, unless otherwise noted. All patients who sign an informed consent and are screened and qualify for the study will be considered enrolled.

⁶ Including melanoma history and prior melanoma treatment history.

⁷ Grade \leq 2 AEs do not need to be reported.

⁸ Only concomitant medications for the treatment of Grade \geq 3 AEs will be captured.

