⁹ CBC with differential should be done 24 to 48 hours after the IMO-2125 injection, to coincide with the post-injection biopsy (if the biopsy is conducted). Chemistry profile and coagulation tests do not have to be conducted if Screening tests were conducted within 7 days of the Cycle 1 Week 1 Visit.

¹⁰PT, aPTT, INR.

¹¹ Blood pressure, heart rate, respiratory rate, and temperature.

¹² Week 2 ECG pre-dose and at 2 hours post-IMO-2125 administration. Week 11 ECG at 2 hours post-IMO-2125 administration.

¹³ Including assessment of melanoma lesions.

¹⁴ In Phase 2, all tumor biopsies are optional. See Section 13.2 of the protocol and the Laboratory Manual for details on the collection of biopsies and analyses of biomarkers.

¹⁵ Biopsy of the injected tumor should occur within 24 to 48 hours after injection (no more than 48 hours).

¹⁶ In Phase 2, blood biomarker samples will be collected from at least 20 patients treated at the IMO-2125 RP2D after which the Sponsor will determine if additional samples are needed. The blood biomarker samples will be collected on Day 1 before IMO-2125 administration, 4 hours after IMO-2125 administration, and 24 to 48 hours (coinciding with the 24-hour PK sample) after the injection. At Week 2 and Cycle 3 Week 8, collect before ipilimumab or pembrolizumab dosing.

¹⁷ Radiologic assessment and Investigator assessment of response at Week 8, Week 17, and Week 29 may be conducted within a \pm 7-day window.

¹⁸ At least every 3 months until progression, start of next melanoma treatment, withdrawal of consent, death, or Sponsor notification that follow up is no longer required.

¹⁹ In Phase 2, response assessed using irRECIST and RECIST v 1.1. Best response to first subsequent treatment should also be captured. Confirmatory scans for CR, PR, and progressive disease should be performed \geq 4 weeks after the date the response was first documented.

²⁰ To minimize bias in the PRO data, the PRO assessments should be completed before study drug administration and AE assessments.

²¹ For patients assigned to the IMO-2125 + pembrolizumab treatment arm, continued pembrolizumab dosing per the approved product label is permitted at the discretion of the Investigator.

²² PK: blood sampling for analysis of plasma concentrations of IMO-2125 and serum concentrations of ipilimumab, and pembrolizumab (See **Error! Reference source not found.**Table 3 of the protocol for specific collection

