8.1.3 Confirmed Response using irRC and irRECIST

Table 7 incorporates the response confirmation rules indicated in the irRC and irRECIST guidelines (see Appendix B and Appendix D).

Table 7 Confirmed Response using irRC or irRECIST

Visit-Level Response	Next Visit-Level Response	Confirmed Response
CR	CR	CR (if visit-level disease assessments are \geq 28 days apart), otherwise SD
CR	PR	PR (if visit-level disease assessments are \geq 28 days apart), otherwise SD
CR	SD	SD
CR, PR, SD	PD	SD
CR, PR	NE	SD
PR	CR, PR	PR (if visit-level disease assessments are \geq 28 days apart); otherwise, SD
PR	SD	SD
SD	SD, CR, PR, PD, NE	SD
PD	PD	PD (if visit-level disease assessments are \geq 28 days apart), otherwise, NE .
CR, PR, SD	No 2 nd visit	SD
PD	No 2 nd visit	NE
NE	No 2 nd visit	NE

The minimum interval for confirmation of CR, PR and PD is 28 days. Subjects must have at least one post-baseline disease assessment to be assigned SD as the best overall response; otherwise, there is no minimum interval for assignment of SD as the best overall response. The same algorithm as for RECIST v1.1 criteria will be used to determine time between disease assessments for confirmation of CR, PR, and PD.

In some situations, it may be necessary to check across more than two sequential time points in order to determine whether or not a minimum duration criteria has been met. The same logic as used for the pairs of time points should be applied. For example, note the following examples.

- For the triplet CR NE CR, if the minimum criteria for CR duration is met for the interval between the two CR assessments, then **Confirmed Response = CR**. Otherwise **Confirmed Response = SD**.
- For the triplet CR CR CR, if the minimum criteria for CR duration is met for the interval between the first and third CR assessments, then **Confirmed Response = CR**. Otherwise **Confirmed Response = SD**.
- For the triplet PR NE PR, if the minimum interval criteria for PR is met for the interval between the two PR assessments, then **Confirmed Response = PR**. Otherwise **Confirmed Response = SD**.
- For the triplet PR PR PR, if the minimum interval criteria for PR is met for the interval between the first and third PR assessments, then **Confirmed Response = PR**. Otherwise **Confirmed Response = SD**.

For confirmed progression using irRC and irRECIST.

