- Indeterminate: Progression has not been determined and one or more non-target sites were not assessed or assessment methods were inconsistent with those used at baseline.

3. New Lesions

The appearance of any new unequivocal malignant lesion indicates PD. If a new lesion is equivocal, for example due to its small size, continued assessment will clarify the etiology. If repeat assessments confirm the lesion, then progression should be recorded on the date of the initial assessment. A lesion identified in an area not previously scanned will be considered a new lesion.

4. Supplemental Investigations

- If CR determination depends on a residual lesion that decreased in size but did not disappear completely, it is recommended the residual lesion be investigated with biopsy or fine needle aspirate. If no disease is identified, objective status is CR.
- If progression determination depends on a lesion with an increase possibly due to necrosis, the lesion may be investigated with biopsy or fine needle aspirate to clarify status.

5. Attentive Progression

Patients requiring discontinuation of treatment without objective evidence of disease progression should not be reported as PD on tumor assessment CRFs. This should be indicated on the end of treatment CRF as off treatment due to Global Deterioration of Health Status. Every effort should be made to document objective progression even after discontinuation of treatment.

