Appendix D: Overall Response Using irRECIST

Response assessment	Description
irCR	
• Complete disappearance of all lesions (and no new measurable or non-measurable lesions).• Pathological lymph nodes (target or non-target) must have diameter <10 mm in short axis.• Requires confirmation by consecutive assessment ≥ 4 weeks after first documentation.
irPR	
• $\geq 30\%$ decrease in tumor burden from baseline.• No unequivocal progression of baseline non-target lesions.• No unequivocal progression of new, non-measurable lesions.• Requires confirmation by consecutive assessment ≥ 4 weeks after first documentation.
irSD	
• Not meeting criteria for irCR or irPR, in absence of irPD.
irPD	
• $\geq 20\%$ increase in tumor burden from nadir (the minimum recorded tumor burden).• The presence of new, measurable lesions does not define progression. New measurable lesions are added to the assessment of tumor burden.• A substantial, unequivocal worsening of baseline non-target lesions is indicative of irPD.• A substantial, unequivocal worsening of new, non-measurable lesions is indicative of irPD.• Requires confirmation by consecutive assessment ≥ 4 weeks after the first documentation.

irCR=immune-related complete response; irPD=immune-related progressive disease; irPR=immune-related partial response; irRECIST=Immune-related Response Evaluation Criteria in Solid Tumors; irSD=immune-related stable disease

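### Section 3.2.2 ends imaging at RECIST v1.1 PD, against the confirmatory-scan footnotes and the irRECIST rules, so irRECIST endpoints are not assured and irRECIST PFS and DoR can be biased upward

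*SAP*

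**What the plan says.** **End of imaging.** Section 3.2.2 of the SAP follows subjects who finish or stop treatment before progression, clinically and radiologically, "until documentation of RECIST v1.1 progressive disease (PD), start of a subsequent anti-cancer treatment regimen" or another listed stop. The next paragraph continues: "After documentation of PD or use of a subsequent anti-cancer treatment regimen, all subjects will be contacted by telephone every 3 months". The abbreviation PD has just been defined there as RECIST v1.1 progressive disease.

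**Schedule footnotes.** Footnote 3 of Tables 4 and 5 reads: "Includes ongoing follow-up every 3 months until documented disease progression, next melanoma treatment". Footnote 19 of Table 4 and footnote 18 of Table 5 also end scans at progression. None of these names a response criterion.

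**Confirmatory scans.** Footnote 20 of Table 4 and footnote 19 of Table 5 state: "Confirmatory scans for CR, PR, and progressive disease should be performed", at least 4 weeks after first documentation.

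**Criteria.** Under RECIST v1.1 (Appendix C), "The appearance of any new unequivocal malignant lesion indicates PD". Under irRECIST (Appendix D), "The presence of new, measurable lesions does not define progression"; such lesions are added to tumor burden. Section 8.1.3 adds: "The minimum interval for confirmation of CR, PR and PD is 28 days".

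**On treatment.** Section 3.2.1 lets treatment run to 29 weeks "in the absence of intolerable toxicity or unequivocal disease progression", again without naming a criterion. Scans are scheduled at Weeks 8, 17 and 29.

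**Use.** Section 2.2 makes irRECIST response a Phase 2 secondary objective. Appendix E plans irRECIST tables for best response, ORR, DRR, DCR, PFS and DoR.

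**The concern.** One criterion ends the imaging, and another, which can need later images, defines a set of secondary endpoints. The document also gives two instructions for the weeks after a RECIST v1.1 PD: move to telephone survival follow-up, or scan again at 4 weeks or later. A site can reasonably follow either.

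If sites follow 3.2.2, the missing scan is not missing at random, because progression itself triggers its absence. Any difference between the RECIST v1.1 and irRECIST results would then partly reflect follow-up rules, and could be read as evidence of immune-type benefit. Different practice between sites would add to this.

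**Working it through.** The plan states no figure on this point, so the check sets the rules side by side and follows subjects through them.

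**1. What happens to a subject not rescanned after RECIST v1.1 PD**

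| Status at that scan | Rule | irRECIST result |
|---|---|---|
| irPD, first post-baseline scan | Table 7, PD with no second visit | NE |
| irPD after an earlier irSD | Table 7, SD then PD | SD |
| irPR for the first time | Table 7, PR with no second visit | SD |
| irPD, for PFS | Section 8.5: unconfirmed irPD is a valid assessment for censoring | Censored at the irPD date |
| irPD after a confirmed irRECIST response, for DoR | Section 8.5: PFS censoring rules apply | Censored at the irPD date |

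Example of the third row: at Week 8 the target lesions shrink and one new measurable lesion appears, with total burden including it down 32%. The new lesion makes this RECIST v1.1 PD. The fall exceeds the 30% in Appendix D, so it is irPR if nothing else has unequivocally progressed. Without a second scan it is scored SD and the possible irRECIST response is lost.

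**2. Direction of the effect on PFS**

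An irPD without a later scan has three possible ends under Section 8.5:
- with no further event, censoring at the irPD date;
- with new anti-cancer therapy first, censoring at its start;
- with death and no new therapy before it, an event at the later death date.

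In none of these is the irPD an event at its own date, so the error is upward each time. DoR uses the same censoring rules.

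**3. Would one more scan be enough to confirm irPD?**

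The scheduled gaps are 17 − 8 = 9 weeks (63 days) and 29 − 17 = 12 weeks (84 days). With the ±7-day window used against us at both ends, the shorter gap is 63 − 14 = 49 days, still above 28. Follow-up scans are about 3 months apart. Any one of these, or the footnoted confirmatory scan, satisfies the interval if it is done.

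**4. Illustration of size (assumptions, not plan figures)**

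Let m of 21 subjects have both RECIST v1.1 PD and irPD at Week 8. A fraction f is rescanned, all of those are confirmed and dated to the first scan, and there is no other event or censoring by then. Just after Week 8, the Kaplan-Meier estimates are:

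- RECIST v1.1 PFS = (21 − m)/21
- irRECIST PFS = (21 − f·m)/21

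| m | RECIST v1.1 | irRECIST, f = 0 | irRECIST, f = 0.5 | irRECIST, f = 1 |
|---|---|---|---|---|
| 8 | 13/21 = 62% | 21/21 = 100% | 17/21 = 81% | 13/21 = 62% |
| 10 | 11/21 = 52% | 21/21 = 100% | 16/21 = 76% | 11/21 = 52% |

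The two criteria agree on every subject here, so the whole gap comes from whether the scan was done.

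**The case against.** A reader might infer that irRECIST responses and confirmed irPD cannot be measured at all, so that the secondary objective cannot be answered. The documents do not support that, for these reasons:

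- **The scan is prescribed.** Both schedules call for it, and it supplies the second assessment that Table 7 needs. Section 3.2.2 describes telephone contact for survival; it neither says that this is the only contact nor forbids a scan.
- **The RECIST-specific stop is narrower than it looks.** It is written for subjects who left or completed treatment before progression. A subject kept on treatment because progression is not judged unequivocal still has the remaining scans at Weeks 17 and 29. The sentence about all subjects pulls the other way, which makes the text ambiguous.
- **Some endpoints do not move.** NE and PD are both non-responses, so irPD scored as NE leaves ORR and DRR unchanged. Section 11.4 also groups the two against disease control. The censoring of unconfirmed irPD is itself a stated rule.
- **The criteria also differ without any RECIST v1.1 PD.** A sum rising from 10 to 12 mm is a 20% increase and meets irPD in Table 8, but the 2 mm rise misses the 5 mm absolute minimum in Appendix C. The imaging stop is not the only source of difference.
- **The protocol is not shown** and may contain a fuller imaging rule.

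All of this stands and limits the finding. It does not remove the conflict inside the SAP. Nor does a single confirmatory scan settle everything: if it does not confirm irPD, 3.2.2 provides no later imaging. DRR needs a response of about 6 months, which one scan some 4 weeks later cannot show.

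**Conclusion.** The concern holds as an internal conflict with consequences for secondary endpoints. Section 3.2.2 and the follow-up footnotes end imaging at progression, while other footnotes and the irRECIST rules call for a scan after it. Where 3.2.2 is followed without a further scan, irRECIST PFS and DoR are biased upward, first-scan irPD becomes NE in the best-response table, and irRECIST responses can be missed where the criteria differ.

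The size cannot be computed from the documents, which give neither a rate of disagreement between the criteria nor a rescan rate. Under the assumed 8 to 10 early progressors of 21, the excess in irRECIST PFS just after Week 8 is f·m-dependent: 38 to 48 percentage points if none is rescanned (8/21 to 10/21), 19 to 24 if half are (4/21 to 5/21), and none if all are rescanned and confirmed. The primary RECIST v1.1 ORR test and its operating characteristics are unaffected. The matter should be corrected, but it does not threaten the primary conclusion.

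**What to change.** 1. Reconcile Section 3.2.2, footnotes 3 and 19 of Table 4, and footnotes 3 and 18 of Table 5 with the confirmatory-scan footnotes (20 in Table 4, 19 in Table 5). State that, for assessment only, a subject with RECIST v1.1 PD who has not started new anti-cancer therapy has the confirmatory scan already called for before moving to telephone follow-up.
2. Name the criterion that ends imaging: RECIST v1.1 PD followed by that one scan, or confirmed irPD. If the former, say that irRECIST PFS, DoR and DRR are truncated there.
3. Keep the first PD date for all RECIST v1.1 endpoints.
4. Add a sensitivity analysis of irRECIST PFS and DoR in which an irPD with no later scan is an event at its first date.

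The cost is wording, one extra analysis and a check that the protocol carries the same rule. The scan in item 1 is already in the schedules, so the downside is that some subjects move to telephone follow-up a few weeks later. Choosing confirmed irPD in item 2 would add scans for subjects whose irPD is not confirmed; the correction does not depend on that choice. No treatment rule changes.
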